We also expect that FFR-guided complete revascularisation during the primary PCI or very shortly thereafter will result in better clinical outcomes compared to revascularisation during a staged procedure based on proven ischemia or symptoms of angina, often nowadays assessed after discharge of the primary event.

Furthermore FFR-guided complete revascularisation approach is expected to significantly reduce the treatment costs and hospitalisation duration as it probably will abolish non-invasive stress testing and re-admissions.

Therefore, we would like to perform a prospective randomised trial in patients with multivessel coronary disease presenting with STEMI that will prove the above mentioned hypothesis and each of the assumptions.

Trial design

We will conduct an investigator initiated prospective randomised clinical trial in all-comer consecutive patients with multivessel coronary artery disease presenting with STEMI and amenable to treatment with primary PCI within < 12 h from the onset of symptoms.

Study population

885 patients with multivessel coronary artery disease presenting with STEMI will be randomised in a 1:2 fashion in this study.

Inclusion Criteria

All patients between 18-85 years presenting with STEMI who will be treated with primary PCI within 12 hours after the onset of symptoms* and have at least one stenosis of $\geq 50\%$ in a non-IRA on QCA or visual estimation of baseline angiography and judged feasible for treatment with PCI by the operator.

*Patients with symptoms for more than 12 hours but ongoing angina complaints can be randomised.

Exclusion Criteria

1. Left main stem disease (stenosis > 50%)
2. STEMI due to in-stent thrombosis
3. Chronic total occlusion of a non-IRA
4. Severe stenosis with TIMI flow \leq II of the non-IRA artery.
5. Non-IRA stenosis not amenable for PCI treatment (operators decision)
6. Complicated IRA treatment, with one or more of the following;
 - Extravasation,
 - Permanent no re-flow after IRA treatment (TIMI flow 0-1),
 - Inability to implant a stent
7. Known severe cardiac valve dysfunction that will require surgery in the follow-up period.
8. Killip class III or IV already at presentation or at the completion of culprit lesion treatment.
9. Life expectancy of < 2 years.
10. Intolerance to Aspirin, Clopidogrel, Prasugrel, Ticagrelor, Heparin, Bivalirudin, or Everolimus and known true anaphylaxis to prior contrast media or bleeding diathesis or known coagulopathy.

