- 1) Clinical outcomes differences between PCI treatment vs optimal medical treatment in patients with at least one FFR positive lesion (group c vs group d)
- 2) Staged PCI versus acute (during PPCI) revascularisation of FFR positive lesions (group a vs group c)
- 3) Optimal Medical Treatment versus PCI treatment of FFR negative lesions (group b + f vs group e)

In order to balance the number of patients in these subgroups we chose for a 1:2 randomisation pattern.

[figure not shown]

Figure 2: Subgroups resulting from this randomisation.

Endpoints

Primary endpoint:

Composite endpoint of all cause mortality non-fatal Myocardial Infarction, any Revascularisation and Cerebrovascular Events (MACCE) at 12 months between groups (a+b versus c-f).

Secondary endpoints:

1. Primary endpoint at 24 and 36 months as well as outcomes of each component of the primary endpoint at 12, 24 and 36 months.
2. Primary endpoint rates at 12, 24 and 36 months in the subgroup of patients receiving staged or acute PCI treatment for FFR positive lesions in the non-IRA vs the subgroup of patients with FFR positive lesion that received optimal medical treatment. {figure 2, subgroups (a+c) vs subgroup d}
3. Primary endpoint rates at 12, 24 and 36 months in the subgroup of patients receiving acute PCI treatment for FFR positive lesions in the non-IRA vs the subgroup of patients receiving staged PCI treatment for FFR positive lesions in the non-IRA (figure 2 subgroups a vs c)
4. Primary endpoint rates at 12, 24 and 36 months in the subgroup of patients receiving staged PCI treatment for FFR negative lesions in the non-IRA vs the subgroup of patients not receiving PCI treatment for FFR negative lesions in the non-IRA. (figure 2 subgroups e vs b+ f)
5. Composite endpoint of Cardiac death, Myocardial Infarction, any Revascularisation, Stroke and Major bleeding at 12, 24 and 36 months (NACE i.e. Net Adverse Clinical Events)
6. A composite of hospitalisation for heart failure and unstable angina pectoris at 12, 24, and 36 months
7. All cause mortality or Myocardial infarction at 12, 24 and 36 months

8. Any revascularisation at 12, 24 and 36 months
9. Stent thrombosis at 12 months, 24 and 36 months
10. Bleeding at 48 hr and 12 months.
11. Treatment costs 12 months, 24 and 36 months

Definitions

Death

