A total sample size of 858 patients (286 in the FFR-guided group, 572 in the control group) is sufficient to obtain a power of at least 80% with a two-sided false positive error rate (alpha) of 5% for rejecting the null-hypothesis of no difference when the endpoint incidence is 8% in the FFR guided group vs 14.5% in the control group, using the Pearson Chi-square test for two proportions assuming an asymptotic normal distribution with a normal approximation method.

Considering a 3% loss in follow-up a total of 885 (295/590) patients will be randomised in this trial. Categorical variables will be assessed with the use of χ^2 or Fisher's exact tests, whereas continuous variables will be assessed with the Wilcoxon rank-sum test.

The results in both groups for the primary endpoint as well as for the secondary endpoints will be presented as time to event curves (Kaplan-Meyer).

Trial Conduct

Cathlab procedure

The primary PCI will be performed within 12 hr after onset of symptoms, however patients with symptoms for more than 12 hr and ongoing ischemia can also be randomised.

Standard care cathlab techniques and equipment will be used to perform the coronary angiography imaging and primary PCI. Artery puncture site is left at the discretion of the operator, although radial approach is strongly recommended to avoid bleeding complications at the puncture site. A diagram or description of the coronary artery tree will be completed at the end of the procedure to indicate which segments have lesions with approximately 50% or more diameter stenosis. If the lesion extends over more than one segment the most proximal segment should be stated.

Assessment of left ventricle function or wall motion abnormalities are at the discretion of local practice.

Thrombosuction and pre-dilation of the lesion are left at the discretion of operator.

Intracoronary injection of nitrates followed by two orthogonal projections for culprit lesion evaluation and stent size choice are strongly recommended.

Stenting should by protocol be performed. Everolimus Eluting Xience V/ Prime /Expedition should be used in this study as these are at the moment the most safe drug-eluting stents clinically proven in this setting.

Post-dilation will be left at the discretion of the operator.

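### Treatment costs fall by default under the Wilcoxon rank-sum rule, which neither tests nor estimates the difference in mean cost per patient

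*Combined protocol and SAP*

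**What the plan says.** All places are in the combined protocol and SAP.

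- **Endpoints**, secondary endpoint 11: "Treatment costs 12 months, 24 and 36 months".
- **Assumptions**: the FFR-guided approach "is expected to significantly reduce the treatment costs and hospitalisation duration". The reason given is that stress tests and readmissions should largely disappear. The section closes by saying that the trial "will prove the above mentioned hypothesis and each of the assumptions".
- **Statistical Considerations**: categorical variables get a chi-square or Fisher's exact test, "whereas continuous variables will be assessed with the Wilcoxon rank-sum test". No exception is made for costs. The one other rule that touches secondary endpoints is that results are shown as Kaplan-Meier curves.

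The documents do not name a mean cost difference, a confidence interval for costs, a costing perspective, unit costs, or a way to handle patients whose cost follow-up is incomplete.

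**The concern.** A claim that a strategy reduces treatment costs is a claim about total spending, and total spending is the mean cost per patient times the number of patients. The Wilcoxon test asks a different question: whether a randomly chosen patient in one arm tends to cost more than a randomly chosen patient in the other. With skewed costs the two answers can differ in strength and even in sign. Kaplan-Meier curves do not estimate a mean cost difference either.

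Two things are at stake. Whatever the data look like, the planned analysis gives a p-value and no size for the saving, so it cannot say how much the strategy saves. And under some cost structures the p-value could contradict the difference in means.

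**Working it through.** **1. The plan's own figure.** The documents give no cost figure, so the only number to reproduce is the sample size. It is not in dispute. With p1 = 0.08, p2 = 0.145, k = 2 and pooled p = (0.08 + 2 × 0.145)/3 = 0.1233:

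n1 = [1.960 × √(1.5 × 0.1233 × 0.8767) + 0.8416 × √(0.08 × 0.92 + 0.145 × 0.855/2)]² / 0.065² = 286 after rounding up.

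This gives 286 + 572 = 858, and 858/0.97 = 885 after rounding up, as stated.

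**2. Inputs from Statistical Considerations.**
- Randomised patients: 295 and 590.
- Primary event rates: "the endpoint incidence is 8% in the FFR guided group vs 14.5% in the control group".
- Staged PCI in controls: half are FFR positive, of whom 70% are revascularised; half are FFR negative, of whom 50% are. So 0.5 × 0.70 + 0.5 × 0.50 = 60%.
- Ischaemia testing in controls: 60% exercise test + 20% nuclear scan = 80%.
- Index non-IRA PCI in the FFR arm: 50%, assuming that the same half-and-half split applies there.

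**3. Assumed inputs.** All prices are assumptions. Base cost is about 100 units (log-normal, log-SD 0.15) and event cost is exponential. Index PCI, staged PCI, mean event cost and test cost are varied. Tests are two-sided at 5%, with 1,000 to 2,000 simulated trials per row. Welch's test stands in for a comparison of means.

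**4. True saving per patient** = (0.6 × staged + 0.145 × event + 0.8 × test) − (0.5 × index + 0.08 × event). For the first row: (12 + 29 + 0) − (15 + 16) = 10.

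| Index / staged / event / test | True saving | Wilcoxon finds it | Test of means finds it |
|---|---|---|---|
| 30 / 20 / 200 / 0 | 10 | 2% (wrong way 5%) | 36–39% |
| 30 / 15 / 300 / 0 | 13.5 | practically never (wrong way 43–48%) | 32–36% |
| 30 / 15 / 300 / 3 | 15.9 | 1% (wrong way 8%) | 44% |
| 30 / 20 / 200 / 5 | 14 | 50% | 58% |
| 30 / 15 / 300 / 5 | 17.5 | 7% (wrong way 1%) | 49% |
| 30 / 20 / 200 / 10 | 18 | 98% | 80% |
| 30 / 15 / 300 / 10 | 21.5 | 74% | 62% |
| 20 / 20 / 200 / 0 | 15 | 77–78% | 68% |
| 30 / 30 / 200 / 0 | 16 | 87% | 70% |
| 30 / 40 / 200 / 0 | 22 | 100% | 88–91% |

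Ranges show the spread between repeat runs.

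**5. A second cost model** (index stay 10 units, index PCI 2, staged PCI 5, testing 0.2 per control, event 10). At the protocol's 60% staged rate, mean costs are about 11.8 and 14.7, and both tests find the saving in 100% of runs. If the staged rate is cut to 20%, which departs from the protocol's assumption, Wilcoxon finds it in 23% and the test of means in 77%.

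**6. The principle in isolation.** Take log-normal costs with equal medians and log-SDs of 0.5 and 0.8. The means are exp(0.125) = 1.133 and exp(0.32) = 1.377, a saving of 1 − 1.133/1.377 = 18%. Wilcoxon is significant in favour of the cheaper arm in 2% of runs, the test of means in 98%.

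**The case against.** The strongest reply is that the protocol's own picture suits a rank test. A reader might infer that the saving sits in the few patients with expensive events, which ranks would largely overlook. The documents do not support that. Assumptions attributes the saving to avoided stress tests and readmissions, and Statistical Considerations implies testing in 80% of controls and staged PCI in 60%. A cost shift across most of an arm is what Wilcoxon detects well, and in the last five rows of the table it beats the test of means.

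The adverse rows also need particular prices: staged PCI cheaper than same-session PCI, and testing free or nearly so. Even there, the test of means finds the saving in only about a third of trials, so a non-significant Wilcoxon result is not damning in itself.

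Finally, the sentence is generic and may have been written for baseline variables. Costs are the last of eleven secondary endpoints, are not powered, and are not among the synopsis's major secondary endpoints. Nothing forbids reporting means alongside the test.

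Most of this stands, and it limits how often the conclusion would be wrong. It does not supply an estimate of the saving. If the sentence was meant only for baseline variables, the cost endpoint has no planned analysis and the same addition is needed.

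**Conclusion.** The point holds as a mismatch between a secondary endpoint and its default analysis. The plan makes a directional claim about costs, and the only rule that reaches them neither tests nor estimates the difference in mean cost. That follows from the text and needs no assumption about prices, beyond taking the mean as the quantity behind a claim about spending.

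The practical harm is conditional. Under the assumed prices it ranges from detection of about 2% against 36% for a test of means, or a wrong-direction result in about 43%, to full agreement with Wilcoxon ahead (74–100% against 62–91% in the last five rows). A reader might conclude that the plan as written will miss or reverse a real saving. The documents do not support that, because they give no unit costs and the result turns on them. The primary analysis and the 858/885 sample size are untouched.

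**What to change.** In Statistical Considerations, exempt treatment costs from the Wilcoxon rule and add a sentence such as: *Treatment costs at 12, 24 and 36 months will be compared as the difference in arithmetic mean cost per patient, with a bootstrap 95% confidence interval and a stated method to account for incomplete follow-up.* Keep Wilcoxon for descriptive continuous variables.

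This is a cheap improvement: a little extra analysis work and no extra patients. The downside is less power than Wilcoxon when the cost difference is spread across most patients. The sentence does not settle the costing perspective, unit costs or resource-use data, which the documents also leave open and which any cost analysis will need.

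### Kaplan-Meier curves are planned for every secondary endpoint, including those that exclude death; with deaths censored they would slightly overstate the absolute risks, and cumulative incidence should replace them there

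*Combined protocol and SAP*

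**What the plan says.** The last sentence of Statistical Considerations sets the method of presentation. It says that results for the primary endpoint "as well as for the secondary endpoints will be presented as time to event curves (Kaplan-Meyer"). It makes no exception for any secondary endpoint. No section names a competing-risk method or says how a death is handled when the endpoint does not include it.

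The Endpoints section lists secondary endpoints that do not contain death:
- the non-fatal parts of "outcomes of each component of the primary endpoint at 12, 24 and 36 months" (item 1);
- "A composite of hospitalisation for heart failure and unstable angina pectoris at 12, 24, and 36 months" (item 6);
- "Any revascularisation at 12, 24 and 36 months" (item 8);
- "Stent thrombosis at 12 months, 24 and 36 months" (item 9), in part.

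The primary endpoint in the same section does contain all-cause death: "Composite endpoint of all cause mortality non-fatal Myocardial Infarction, any Revascularisation and Cerebrovascular Events (MACCE) at 12 months". So do its 24- and 36-month versions, the FFR subgroup comparisons built on it (items 2 to 4), and death or MI (item 7). NACE (item 5) contains cardiac death only.

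Testing is described separately. "Categorical variables will be assessed with the use of" chi-square or Fisher's exact tests, and continuous variables are compared with the Wilcoxon rank-sum test. No log-rank test or Cox model is named.

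**The concern.** Kaplan-Meier treats a censored patient as someone who could still have the event later. That is reasonable for a patient lost to follow-up, but not for one who has died. When deaths are censored, one minus Kaplan-Meier estimates the risk in a population where nobody dies, and this is higher than the proportion of trial patients who have the event. The gap widens as deaths accumulate towards 36 months.

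What is at stake is the reported absolute risk of each component. Revascularisation matters most here. Statistical Considerations attribute the excess events expected in FFR-positive patients on medical treatment mainly to unplanned revascularisations, so readers will look to that curve to explain the primary result.

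**Working it through.** **1. The plan's own figure.** Inputs from Statistical Considerations: 8% vs 14.5%, allocation 1:2, two-sided 5%, power 80%. The pooled proportion is (0.08 + 2 × 0.145)/3 = 0.1233. Using the pooled formula without continuity correction:

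n(FFR) = [1.960 × √(1.5 × 0.1233 × 0.8767) + 0.842 × √(0.08 × 0.92 + 0.145 × 0.855/2)]² / 0.065² = 286.

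This gives 286 + 572 = 858, and 858/0.97 = 885 after rounding up. Both match the plan. The calculation uses primary-endpoint proportions only, so the choice of curve for secondary endpoints does not enter it.

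**2. Which endpoints are exposed.** Setting the Endpoints list beside the Definitions:
- Fully exposed: single MI, revascularisation and cerebrovascular components; any revascularisation; hospitalisation for heart failure or unstable angina; definite stent thrombosis.
- Partly exposed: probable and possible stent thrombosis, because unexplained deaths count as events (within 30 days for probable, to the end of follow-up for possible). Only explained deaths compete.
- Barely exposed: NACE, because a death is cardiac unless an unequivocal non-cardiac cause is established.
- Not exposed: MACCE as listed under Endpoints; all-cause death or MI.

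**3. Size of the excess.** Let D be the cumulative risk of death and C the true cumulative incidence of the event. With constant hazards, the death hazard is d = −ln(1 − D). The event hazard h solves

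C = [h/(h + d)] × [1 − exp(−(h + d))],

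and the Kaplan-Meier reading is 1 − exp(−h). If all deaths came before any event, the reading would be C/(1 − D), which is the upper bound.

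The documents give no death rate. Among the single non-fatal endpoints they give a rate only for stroke (1.0% and 1.5%). C and D below are therefore assumptions.

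| Horizon | C | D | Kaplan-Meier reads | Excess (points) | Bound C/(1 − D) |
|---|---|---|---|---|---|
| 12 months | 5% | 2% | 5.05% | 0.05 | 5.10% |
| 12 months | 11% | 2% | 11.11% | 0.11 | 11.22% |
| 12 months | 10% | 3% | 10.15% | 0.15 | 10.31% |
| 36 months | 20% | 2% | 20.20% | 0.20 | 20.41% |
| 36 months | 20% | 5% | 20.50% | 0.50 | 21.05% |
| 36 months | 20% | 8% | 20.81% | 0.81 | 21.74% |

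The 12-month values were chosen to fit inside the plan's composites. Adding the plan's stroke rates and ignoring overlap, 5 + 2 + 1 = 8% in the FFR arm, and 11 + 2 + 1.5 or 10 + 3 + 1.5 = 14.5% in the control arm.

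**4. Effect on the contrast.** Take true risks of 5% and 11%: difference 6.00 points, ratio 2.20.
- Deaths 5% in both arms: readings 5.13% and 11.28%, difference 6.15, ratio 2.20.
- Deaths 5% and 8%: readings 5.13% and 11.46%, difference 6.33, ratio 2.23.

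**5. Against sampling error.** The 95% half-width is 1.96 × √[p(1 − p)/n]. With 295 and 590 patients it is 3.4 and 2.4 points at 10%, and 4.6 and 3.2 points at 20%.

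**The case against.** The strongest reply is that the sentence governs display, and that the excess is small beside sampling error. Both parts stand. The only tests named work on proportions, in which a patient followed until death without the event counts as event-free. A reader might infer that the planned comparisons or p-values are biased; the documents do not support that, because no named test rests on the curves.

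Other stronger readings also fail:
- *That the risks are certain to be overstated.* The plan does not say that deaths are censored. That is ordinary practice, but here it is an inference.
- *That stent thrombosis and NACE are affected throughout.* The Definitions count unexplained deaths as probable or possible stent thrombosis and classify unclear deaths as cardiac, so most of the problem is absent there.
- *That the curves would disagree with the tabulated proportions for this reason.* Loss to follow-up, planned at 3%, separates any censoring-based curve from crude proportions. That includes the primary composite and an Aalen-Johansen curve.
- *That the curves would mislead about which component drives the result.* With equal mortality the ratio does not move. Unequal mortality is possible, and the DSMB is asked to watch for it, but the plan does not predict it.

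What remains is that a stated method is the wrong estimator of absolute risk for a definable set of endpoints, at horizons up to 36 months, and that the remedy is cheap.

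**Conclusion.** The point holds as a minor reporting matter. If deaths are censored, Kaplan-Meier slightly overstates the absolute risk of endpoints that exclude death. Under the assumed rates the excess is about 0.05 to 0.15 points at 12 months and up to about 0.8 points at 36 months (20% risk, 8% deaths, constant hazards). If every one of those deaths preceded the events, the 36-month excess would reach 1.7 points. The between-arm contrast changes little unless mortality differs by arm.

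The exemption of the primary endpoint relies on the Endpoints section, which includes all-cause death. The opening sentence of Statistical Considerations names cardiac death instead. That conflict needs its own reconciliation; if cardiac death were the intended component, unequivocally non-cardiac deaths would compete with the primary composite too.

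**What to change.** Amend the Kaplan-Meier sentence in Statistical Considerations. Keep Kaplan-Meier for MACCE as defined under Endpoints and for all-cause death or MI. For every endpoint that does not include all-cause death, present cumulative incidence (Aalen-Johansen), with any death outside that endpoint treated as a competing event and loss to follow-up as censoring. Stating the rule by endpoint content also settles the stent thrombosis categories, NACE and bleeding at 12 months without listing each one. Gray's test or cause-specific hazard ratios are not needed for this change.

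The cost is one sentence and a standard routine. The small downside is two types of curve in one report, which a figure footnote can explain. Sample size, data collection and the named tests stay as they are.

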For ethical and safety reasons, three formal interim analyses will be performed when 25%, 50% and 75% of the suspected number of primary endpoint events in patients allocated to FFR guided revascularisation group or the actual standard of care group have occurred (i.e. after 32, 63 and 95 events, respectively). The independent Data Safety Monitoring Board (DSMB) will review these analyses and inform the Steering Committee. The DSMB will consider the primary endpoint and secondary endpoints consistency, and the consistency of treatment effects across clinically relevant subgroups.

The DSMB will also monitor the study to evaluate if each of the two groups is associated with increased mortality. For these safety analyses, premature termination of the trial should be considered.

The DSMB will consist of 3 members.

First 5 patients in all centres will be fully monitored for all variables.

This will be followed by spot monitoring aiming at a site monitoring for a total of 25% of trial population for 100% of variables and for the rest of the population for 20% of the variables.

Event collection will be done by patients contacts or monitoring of patient charts up to 1 year at 30 and 360 days. Thereafter, event collection will be done by correspondence or telephone contact with all patients at 2 and 3 years. In parallel to this, information from national health registers in respective countries will be used.

Events will be analysed by an independent CRO and will be adjudicated by an independent Clinical Evaluation Committee (CEC).

All sites will undergo training prior to study initiation. Training will cover how to obtain informed consent, randomisation, data entry, the catheter laboratory procedure for guide wire based coronary pressure measurement, and how to complete the electronic case record. Training could be delivered either by a Site Visit or through a single meeting attended by PIs and support staff from all of the sites.

Study duration

The study is expected to finish enrolment in 3.5 years (+/- 2) months from the start date.

We aim to produce the first manuscript (30 day results) at 45 (+/-1) months after the start of the study. The main manuscript is expected at 55 (+/-1) months after the start of the study.

Regulatory approvals

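### For event endpoints the plan names only crude-proportion tests but displays Kaplan-Meier curves, so test and curve treat incompletely followed patients differently, and the curves overstate endpoints that exclude all-cause death

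*Combined protocol and SAP*

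**What the plan says.** The Endpoints section defines the primary endpoint as a composite of all-cause mortality, non-fatal MI, any revascularisation and "Cerebrovascular Events (MACCE) at 12 months between groups (a+b versus c-f").

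Statistical Considerations calculates the sample size "using the Pearson Chi-square test for two proportions assuming an asymptotic normal distribution with a normal approximation method". Its general rule is "Categorical variables will be assessed with the use of χ^2 or Fisher's exact tests", with the Wilcoxon rank-sum test for continuous variables. It expects 3% loss to follow-up and raises 858 patients to 885 for it. Results for the primary and secondary endpoints "will be presented as time to event curves (Kaplan-Meyer").

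No log-rank test, Cox model or comparison of Kaplan-Meier estimates is named. The abbreviation HR appears only in the list of abbreviations. Nothing says how a patient without known 12-month status enters the chi-square test, and no competing-risk method is mentioned.

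Trial management collects events by patient contact or chart monitoring "up to 1 year at 30 and 360 days", then by contact at 2 and 3 years, with national health registers used in parallel. The Synopsis gives the visit as 12 months. On timing, Study duration says "The study is expected to finish enrolment in 3.5 years (+/- 2) months from the start date" and "The main manuscript is expected at 55 (+/-1) months after the start of the study". No data cut-off or minimum follow-up is given.

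**The concern.** A chi-square or Fisher test on 12-month status needs that status for every patient in the denominator. For a patient lost at month 5 the analyst must drop the patient, count the patient as event-free, or keep the patient only if an event was seen before the loss. The plan does not choose. The Kaplan-Meier curve makes its own choice: it uses the patient up to month 5 and then censors. The reported p-value and the 12-month rates read off the curve then need not agree, and the rule could be chosen after the data are seen, in a trial where treatment is not masked and revascularisation counts as an event.

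The second issue concerns the secondary endpoints. One minus Kaplan-Meier with deaths censored estimates incidence as if nobody died. It is too high for revascularisation, MI, stroke, stent thrombosis and bleeding, and the error grows towards 36 months.

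**Working it through.** **1. The plan's own figure.** Inputs from Statistical Considerations: p1 = 0.08 (FFR-guided), p2 = 0.145 (control), two-sided alpha 0.05, power 0.80, allocation 1:2. The pooled proportion is (0.08 + 2 × 0.145)/3 = 0.1233.

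n1 = [1.960 × √(1.5 × 0.1233 × 0.8767) + 0.8416 × √(0.08 × 0.92 + 0.145 × 0.855/2)]² / 0.065²
= [1.960 × 0.4027 + 0.8416 × 0.3682]² / 0.004225 = 1.2083/0.004225 = 286.0.

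This gives 286 + 572 = 858, and 858/0.97 = 884.5, so 885. Both figures reproduce.

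**2. Power of a complete-case chi-square with the planned loss.** 885 × 0.97 = 858 patients, hence 80.0% power. The inflation does what it was meant to do.

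**3. How much the unstated rule moves the primary difference.** Assume 3% loss in each arm, with loss and event times spread evenly over the year. Half of the events in lost patients are then unseen.

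| Rule | Control | FFR-guided | Difference (points) |
|---|---|---|---|
| Complete case | 14.5% | 8.0% | 6.5 |
| Lost counted as event-free: 0.985p | 14.28% | 7.88% | 6.40 |
| Event or full follow-up: 0.985p/(0.97 + 0.015p) | 14.69% | 8.11% | 6.58 |
| Kaplan-Meier | 14.5% | 8.0% | 6.5 |

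In simulation with 3% loss, the Kaplan-Meier difference has about 1-1.5% less variance than the complete-case difference. Log-rank and chi-square fall on opposite sides of p = 0.05 in about 1% of simulated trials. Power is 81.1% for log-rank and 81.4% for chi-square.

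If loss differs by arm (assumed 0% FFR-guided and 4.5% control, or 6% and 1.5%), chi-square power runs from 0.78 to 0.84 according to the rule, against about 0.81 for log-rank. Type I error stays near 5% in all scenarios (0.048 to 0.056).

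**4. Timeline.** Enrolment ends at month 40 to 44 and the main manuscript comes at month 54 to 56. The nominal gap is 55 − 42 = 13 months. Taking the manuscript date as the data cut, the gap is below 12 months for only two pairings of the stated limits and midpoints:
- 44 and 54: 10 months, so 2 × 885/44 ≈ 40 patients short under uniform accrual;
- 44 and 55: 11 months, so about 20 patients short.

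If the cut comes before the manuscript, the margin shrinks. An assumed lag of 1 month on the nominal dates leaves nobody short; a lag of 3 months leaves 2 × 885/42 ≈ 42 short.

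**5. Day 360.** Expected events in 885 patients are 295 × 0.08 + 590 × 0.145 = 109.2. Under an even spread, 5/365 of these, about 1.5, fall after day 360.

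**6. Competing risk of death.** With roughly constant hazards, one minus Kaplan-Meier exceeds the cumulative incidence by about F × m/2, where F is the Kaplan-Meier component rate and m is mortality. The documents give neither, so both are assumed:
- 1 year, F = 10%, m = 2-4%: 0.1 to 0.2 points;
- 3 years, F = 17-20%, m = 6-10%: 0.17 × 0.06/2 = 0.5 to 0.20 × 0.10/2 = 1.0 points.

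The primary endpoint, as the Endpoints section defines it, includes all-cause death and is not affected.

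**The case against.** The case for leaving the plan as it is has weight. The endpoint is a 12-month proportion, the chi-square test matches the sample-size method exactly, and the 3% inflation already protects its power. A Kaplan-Meier display beside a fixed-time test is not a contradiction. Registers, chart checks and later contacts will settle the 12-month status of many patients, and they partly cover days 361 to 365. The competing-risk point does not touch the primary endpoint. All of this stands, and it is why the effect on the primary result is small.

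Three stronger readings are tempting and are not supported:

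- **That the trial falls below its planned power, to about 78%, or that its 6.5-point difference is inflated to about 6.8.** Both figures need some 40 patients short of 12 months in addition to the 3% loss. That requires the latest enrolment end (month 44) with a data cut at the earliest manuscript date (month 54). Late enrolment with a late manuscript (44 and 56) leaves 12 months. The dates are publication targets, and no text plans an analysis before 12 months.
- **That test and curve rest on different data.** They use the same patients and events. Only the treatment of incompletely followed patients differs.
- **That only crude-proportion tests are named at all.** This is true for event endpoints; the Wilcoxon test is named for continuous variables.

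The objection leaves two gaps open: the rule for patients with unknown status is missing, and Kaplan-Meier is the wrong estimator for endpoints that exclude all-cause death.

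**Conclusion.** The point holds as a gap in specification and a choice of estimator. It is not a wrong figure: 858 and 885 are correct.

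For the primary endpoint the consequence is small. With 3% loss balanced between arms, the possible rules put the difference between 6.4 and 6.6 points, and complete-case power stays at 80%. The rule matters more only if loss differs by arm, which is an assumption. A shortfall in 12-month follow-up arises only at the edge of the stated timeline tolerances, or if the data cut precedes the manuscript by more than about a month, also an assumption. The day-360 contact concerns about 1.5 of 109 expected events.

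For the secondary endpoints that exclude all-cause death, the curves overstate incidence by about 0.1 to 0.2 points at 1 year and 0.5 to 1.0 points at 3 years, under the assumed component rates and mortality. The change is worth making because it costs almost nothing and closes an analysis choice before the data are seen.

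**What to change.** 1. Define the primary analysis as the between-arm difference in the Kaplan-Meier estimate of MACCE at 12 months (day 365 from randomisation), with a 95% CI and a z-test from the same Greenwood variances. With complete follow-up this equals the difference in crude proportions, so the estimand does not change. The test is not identical to Pearson's, because its variance is not pooled. With 286 and 572 patients the planning formula gives 0.065/√(0.0736/286 + 0.1240/572) = 2.985, hence Φ(2.985 − 1.960) ≈ 85% power. The planned 885 therefore suffice. Use the same method for MACCE at 24 and 36 months. A log-rank test, or a chi-square test with a stated rule for unknown status, would also close the gap; the fixed-time difference stays closest to the plan.
2. Report revascularisation, MI, stroke, stent thrombosis and bleeding as cumulative incidence with death as a competing event, at all time points. Treat other secondary endpoints that exclude all-cause death in the same way; for NACE, which counts cardiac death, the competing event is non-cardiac death.
3. Ascertain events through day 365, by moving the contact or by completing status from charts and registers.
4. Lock the data for the main report only after the last patient's 12-month contact.

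Cost: a few sentences in the SAP, a five-day shift of one contact, and slightly more programming. No extra patients. If enrolment ends late, the main manuscript may have to follow.
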